5.1 Agent Administration

5.1.1 MLN0128 (TAK-228)

Patients will receive MLN0128 (TAK-228) orally daily on days 1-21 every 28-day cycle. Patients will complete a pill diary and return at each visit. Leftover study medication will also be returned.

Treatment will be administered on an outpatient basis, but inpatient status is allowed too. Reported adverse events and potential risks are described in Section 7. Appropriate dose modifications are described in Section 6. No investigational or commercial agents or therapies other than those described below may be administered with the intent to treat the patient's malignancy.

Antiemetics and antidiarrheal agents are not required but may be administered as needed for symptom control.

If severe emesis or mucositis prevents the patient from taking scheduled doses, that dose will be skipped. If emesis occurs after study medication ingestion, the dose will not be readministered, and patients should resume dosing at the next scheduled time with the prescribed dosage. Patients should record the occurrence of the emesis in their dosing diaries. Under no circumstance should a patient repeat a dose or double-up doses.

5.1.2 Intrathecal chemotherapy:

5.1.2.1 For patients without known CNS involvement:

Within one week (at most ten days) prior to start of therapy, patients will receive mandatory CSF prophylaxis consisting of an intrathecal regimen according to institutional or national guidelines, e.g., methotrexate 12 to 15 mg and/or cytosine arabinoside 40 mg or dexamethasone 4 mg or equivalent steroid dose. In case of

anticipated safety risks caused by lumbar puncture, e.g., in case of thrombocytopenia, CSF prophylaxis may be omitted.

5.1.2.2 For patients with CNS involvement:

Intrathecal (IT) chemotherapy (methotrexate 12 to 15 mg and/or cytarabine 100 mg) can be given for patient with malignant CSF (involved with ALL by morphology or flow cytometry) due to poor penetration of MLN0128 (TAK-228) to CSF. Treatment will be as per standard practice of each participating institution.

5.2 General Concomitant Medication and Supportive Care Guidelines

As indicated in Section 2.2.5, MLN0128 (TAK-228) has low potential for interaction with other drugs based on its limited ability to induce or inhibit cytochrome P450 isoenzymes. Therefore, there are no proscriptions against particular concomitant medications.

Supportive care: transfusions with packed RBC or platelets will be done as per each local participating institution guidelines.

G-CSF: Treatment with filgrastim (5 mcg/kg SC daily until ANC > 5000) or Pegfilgrastim (6 mg SC x1) will be allowed if severe neutropenia exists or is suspected to occur. The start date will be left to the judgment of the treating physician, but dates of administration are to be recorded in the case report forms.

Management of Hyperglycemia

On the basis of the clinical experience in TAK-228 trials, most episodes of hyperglycemia observed occurred within the first 60 days after initiation of treatment with TAK-228 and have been either Grade 1 or Grade 2, and have responded quickly to oral metformin. Hyperglycemia has not been dose-limiting since the institution of a standard regimen for early treatment of hyperglycemia.

All patients developing hyperglycemia during the study should have their glucose closely monitored by study staff. The investigator may choose to continue close monitoring of patients who develop Grade 1 hyperglycemia (fasting glucose >ULN \leq 160 mg/dL) or, alternatively, consider initiating treatment with an oral hypoglycemic agent, such as metformin. All patients with \geq Grade 2 hyperglycemia (fasting glucose $>$ 160 mg/dL) must be treated aggressively with oral hypoglycemic agents and/or insulin as clinically indicated. The investigator should consult an endocrinologist, if needed, to aid in optimizing the patient's hyperglycemia treatment plan.

It is recommended that patients with elevated fasting blood glucose be initially treated with a fast acting insulin sensitizer such as metformin at 500 mg orally QD and titrate up to a maximum of 1000 mg orally BID as needed. Concurrent addition to metformin of DPP-4 inhibitors (e.g., sitagliptin or vildagliptin) and/or insulin should also be

considered. Oral sulfonylureas (e.g., glipizide or glyburide) should be used with caution, due to the higher risk of inducing hypoglycemia in patients. The dose of oral hypoglycemic agents should be adjusted in patients with renal insufficiency. In addition, patients should be encouraged to follow a low carbohydrate diet once hyperglycemia is first observed.

If any fasting serum glucose reading performed at the site indicates hyperglycemia ($>$ ULN or ≥ 110 mg/dL), the study staff should first confirm that the patient was fasting at the time of blood specimen collection (ie, nothing by mouth for at least 8 hours before collection).

In-Home Daily Fasting Glucose Monitoring

In addition to obtaining fasting glucose levels at the clinic visits as outlined in the Schedule of Events, all patients receiving TAK-228 will be given a glucometer to monitor their daily fasting blood glucose levels at home. The level should be collected daily, predose on dosing days, and at approximately the same time each day.

On Cycle 1 Day 1, the patient will be provided an in-home glucometer. Patients should be trained on proper use of the glucometer and instructed to collect a daily fasting blood glucose level every morning (predose on dosing days), starting on Cycle 1 Day 2. Patients will be instructed to bring the glucometer with them to each study visit so that the data collected can be reviewed and recorded in the source documents. Investigators will be responsible for reviewing the home glucose monitoring logs for hyperglycemia.

The patient will be instructed to contact the site immediately if the value is abnormal (ie, ≥ 150 mg/dL) for further instructions on the management of their hyperglycemia. Hyperglycemia observed during home glucose monitoring should be confirmed in the clinic.

If no irregularities in the fasting blood glucose level are observed during a minimum of 2 consecutive months, then the frequency of in-home fasting blood glucose testing can be reduced to a minimum frequency of once weekly, depending on the investigator's judgment and approval. Patients will continue to notify the investigator of fasting blood glucose levels that exceed 150 mg/dL and, if blood glucose levels are not well controlled or if the patient requires either oral hypoglycemic agents or insulin to control blood glucose levels, then the frequency of in-home testing of fasting blood glucose levels will be reinstated to daily.

5.3 Duration of Therapy

In the absence of treatment delays due to adverse event(s), treatment may continue after response until one of the following criteria applies:

- Disease progression at any time,

- Intercurrent illness that prevents further administration of treatment,
- Unacceptable adverse event(s),
- Patient decides to withdraw from the study,
- General or specific changes in the patient's condition render the patient unacceptable for further treatment in the judgment of the investigator.
- No response after 6 cycles of MLN0128 (TAK-228). Response includes CR/CRi/PR or MLFS on bone marrow
- Dose delay of more than 1 cycle due to related toxicity or more than 2 cycles to unrelated toxicity
- If responding, patient proceeds with allogeneic stem cell transplant.

5.4 Duration of Follow Up

Patients will be followed for toxicity for 1 month after removal from study or until death, whichever occurs first. Patients removed from study for unacceptable adverse event(s) will be followed until resolution or stabilization of the adverse event. Patients will be followed for survival status by a telephone call every 3 months unless patient refuses. Patients will be followed periodically until death by using public health records, for example, a local newspaper.

5.5 Criteria for Removal from Study

Patients will be removed from active treatment when any of the criteria listed in Section 5.3 applies. The reason for removal from active treatment and the date the patient was removed must be documented in the Case Report Form.

6. DOSING DELAYS/DOSE MODIFICATIONS

Dose de-escalation will be pursued if patients develop a significant related AE as below.

Dose escalation could be chosen if patients fail to show a response (CR/CRi/ MLFS) and show no evidence of drug-related toxicity. Dose escalation or re-escalation will be done after a dose has been tolerated for 2 cycles.

Dose delays are allowed for a maximum of 1 cycle if patient develops a related toxicity and 2 months if unrelated toxicity (disease related for example).

Dose Level	MLN0128 (TAK-228) Dose
-2	2 mg orally Monday-Friday, weeks 1 - 3 of each 28-day cycle
-1	2 mg orally days 1 - 21
0	3 mg orally days 1 - 21
+1	4 mg orally days 1 - 21
+2	4 mg orally days 1 - 28

Note: All treatment modifications must be expressed as a specific dose or amount rather than as a percentage of the starting or previous dose.

Nausea	Management/Next Dose for MLN0128 (TAK-228)
≤ Grade 1	No change in dose
Grade 2	Hold until ≤ Grade 1. Resume at same dose level.
Grade 3	If experienced for ≤ 72 hours, hold MLN0128 (TAK-228) until ≤ Grade 1, then resume MLN0128 (TAK-228) without dose modification. If experienced for > 72 hours despite optimal therapy, hold MLN0128 (TAK-228) until ≤ Grade 1, then resume treatment with the dose of MLN0128 (TAK-228) reduced by 1 level.
Grade 4	Off protocol therapy

*Patients requiring a delay of > 4 weeks if related to MLN0128 (TAK-228) should go off protocol therapy.

Vomiting	Management/Next Dose for MLN0128 (TAK-228)
≤ Grade 1	No change in dose
Grade 2	Hold until ≤ Grade 1. Resume at same dose level.
Grade 3	If experienced for ≤ 72 hours, hold MLN0128 (TAK-228) until ≤ Grade 1, then resume MLN0128 (TAK-228) without dose modification. If experienced for > 72 hours despite optimal therapy, hold MLN0128 (TAK-228) until ≤ Grade 1, then resume treatment with the dose of MLN0128 (TAK-228) reduced by 1 level.
Grade 4	Off protocol therapy

*Patients requiring a delay of > 4 weeks if related to MLN0128 (TAK-228) should go off protocol therapy.

Diarrhea	Management/Next Dose for MLN0128 (TAK-228)
≤ Grade 1	No change in dose
Grade 2	Hold until ≤ Grade 1. Resume at same dose level.
Grade 3	Hold* until < Grade 2. Resume at one dose level lower
Grade 4	Off protocol therapy
*Patients requiring a delay of > 4 weeks if related to MLN0128 (TAK-228) should go off protocol therapy.	
**Patients requiring > two dose reductions should go off protocol therapy.	
Recommended management: Loperamide antidiarrheal therapy Dosage schedule: 4 mg at first onset, followed by 2 mg with each loose motion until diarrhea-free for 12 hours (maximum dosage: 16 mg/24 hours) Adjunct anti-diarrheal therapy is permitted and should be recorded when used.	

Hyperglycemia	Management/Next Dose for MLN0128 (TAK-228)
≤ Grade 1	No change in dose. Optimize blood sugar control. *
Grade 2	No change in dose. Optimize blood sugar control.
Grade 3 Asymptomatic	No change in dose. Optimize blood sugar control.
Grade 3 Symptomatic or >7 days on therapy	Hold** until < Grade 2. Resume at one dose level lower.
Grade 4	Off protocol therapy
* If medical therapy is needed, metformin is preferred unless contraindicated. Sulfonylurea can be added if metformin does not control blood glucose level. If this fails to bring it to ≤ G1 within 1 month, then oral hypoglycemics can be stopped and insulin used.	
**Patients requiring > two dose reductions should go off protocol therapy.	
Hyperglycemia will be based on fasting glucose level.	

Thrombocytopenia and neutropenia	Management/Next Dose for MLN0128 (TAK-228)
≤ Grade 1	No change in dose
Grade 2	Hold until ≤ Grade 1. Resume at same dose level.
Grade 3	Hold* until ≤ Grade 1. Resume at one dose level lower
Grade 4	Off protocol therapy
This dose modification for thrombocytopenia and neutropenia only pertains to	

Thrombocytopenia and neutropenia	Management/Next Dose for MLN0128 (TAK-228)
	patients in remission. Thrombocytopenia and neutropenia will not be considered dose limiting during remission induction.
	*Patients requiring a delay of >4 weeks if related to MLN0128 (TAK-228) should go off protocol therapy. This only will be counted if patients are in remission (CR).
	**Patients requiring > two dose reductions should go off protocol therapy.

Non-hematological toxicity:

Non-hematological toxicities of fatigue, electrolyte abnormalities and abnormal liver function tests, including bilirubin, transaminases and alkaline phosphatase will only require dose modification if they are likely or definitely related to MLN0128 (TAK-228) and persist more than 7 days. Neutropenic fever and infectious toxicities are only counted for if patients achieve remission and then develop these adverse events.

Non-Hematological Toxicity

Event	Management/Next Dose for MLN0128 (TAK-228)
≤ Grade 1	No change in dose
Grade 2	Hold until ≤ Grade 1. Resume at same dose level.
Grade 3	Hold* until Grade 1. Resume at one dose level lower
Grade 4	Patients who develop Grade 4 nonhematologic toxicities (with the exception of isolated non-clinically significant laboratory values) should permanently discontinue study treatment, unless they derive clinical benefit, in which case they may be retreated at a reduced dose level after recovery to ≤ Grade 1 severity.

**Patients requiring a delay of >4 weeks if related to MLN0128 (TAK-228) should go off protocol therapy.

**Patients requiring > two dose reductions should go off protocol therapy.

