A death on INK128-001 due to ventricular arrhythmia and cardiac arrest was assessed as possibly related to MLN0128 (TAK-228). After discussion with the FDA, study C31002, a phase 1 single-arm study to evaluate the effect of a single dose of 40 mg MLN0128 (TAK-228) on the QT/QTc interval was initiated in patients with advanced solid tumors. After completing the per-protocol PK/ECG/cardiac contractility monitoring, the patients continued MLN0128 (TAK-228) 30 mg QW with continued cardiac monitoring. The study results showed that treatment with MLN0128 (TAK-228) was not associated with clinically meaningful effects on the overall electrocardiographic safety profile, and that ECHO/MUGA at screening is not required on MLN0128 (TAK-228) trials. Takeda and CTEP have agreed that ECG monitoring should be performed on patients prior to entering MLN0128 (TAK-228) trials, at the time of completing treatment with MLN0128 (TAK-228), and periodically during the trial when clinically appropriate.

In INK128-002, which was reported by Ghobrial *et al.* (17) MLN0128 (TAK-228) was administered orally to 37 patients in two different schedules, either daily or three days on/four days off every week schedule with 28-day cycles. The maximum tolerated dose (MTD) was 6 mg for the daily schedule and was not defined in the 3 days on/four days off schedule. Common side effects included nausea (56%), fatigue (49%), hyperglycemia (38%), thrombocytopenia (36%), diarrhea (28%), anorexia (23%), emesis (23%), stomatitis (21%), anemia (21%), and constipation (18%). 27% discontinued drug due to an adverse event. Among 27 patients evaluable for confirmed responses, 1 multiple myeloma patient (7 mg QD) achieved a major response lasting 2 months, and 13 myeloma patients (2 at 2 mg QD, 4 each at 4 mg QD and 7 mg QD, 2 at 9 mg QDx3d QW, and 1 at 12 mg QDx3d QW) and 2 Waldenstrom's macroglobulinemia patients (at 6 mg QD and 9 mg QDx3d QW) had stable disease.

Subsequent experience with the daily schedule has indicated that MLN0128 (TAK-228) at 6 mg/day is intolerable for prolonged administration in some patients ([name], personal communication). Accordingly, the recommended phase 2 dose is 5 mg/day for daily administration.

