3.2 Exclusion Criteria

- 3.2.1 Patients who have had chemotherapy or radiotherapy \leq 4 weeks prior to entering the study or those who have not recovered from adverse events due to agents administered more than 4 weeks earlier. Treatment with glucocorticoids, hydroxyurea, and tyrosine kinase inhibitors is allowed up to 24 hour prior to initiation of therapy.
- 3.2.2 Patients with WBC > 30,000 are not eligible to start therapy. However, it is permissible to use glucocorticoids and/or hydroxyurea to diminish peripheral WBC to less than 30,000 provided these agents are stopped at least 24 hours prior to the first dose of MLN0128 (TAK-228).
- 3.2.3 Patients who are receiving any other investigational agents.
- 3.2.4 Patients with known other active cancers. Skin cancers (basal or squamous) are exempted.
- 3.2.5 History of allergic reactions attributed to compounds of similar chemical or biologic composition to MLN0128 (TAK-228).
- 3.2.6 Because of the reportedly low potential for interaction with agents that induce or inhibit cytochrome P450 enzymes (summarized in Section 2.2.5), there are no prohibitions of specific medications on the basis of anticipated drug-drug interactions.

3.2.7 Uncontrolled intercurrent illness including, but not limited to, ongoing or active infection, symptomatic congestive heart failure, hypertension, unstable angina pectoris, cardiac arrhythmia, or psychiatric illness/social situations that would limit compliance with study requirements. No ischemic myocardial or cerebrovascular event, placement of pacemaker, or pulmonary embolism within six months of receiving first dose of MLN0128 (TAK-228).

3.2.8 Any patient receiving chronic corticosteroid administration prior to study enrollment is ineligible.

3.2.9 Baseline prolongation of the rate-corrected QT interval (QTc) > 480 milliseconds or history of congenital long QT syndrome or Torsades de pointes.

3.2.10 Concomitant administration of any proton pump inhibitor (PPI) is not permitted during the study. Patients receiving PPI therapy before enrollment must stop using the PPI for 7 days before their first dose of study drugs.

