7.1.1 CAEPR for MLN0128 (TAK-228)

Comprehensive Adverse Events and Potential Risks list (CAEPR) for MLN0128 (TAK-228) (INK128, NSC 768435)

The Comprehensive Adverse Events and Potential Risks list (CAEPR) provides a single list of reported and/or potential adverse events (AE) associated with an agent using a uniform presentation of events by body system. In addition to the comprehensive list, a subset, the Specific Protocol Exceptions to Expedited Reporting (SPEER), appears in a separate column and is identified with bold and italicized text. This subset of AEs (SPEER) is a list of events that are protocol specific exceptions to expedited reporting to NCI (except as noted below). Refer to the 'CTEP, NCI Guidelines: Adverse Event Reporting Requirements'
http://ctep.cancer.gov/protocolDevelopment/electronic_applications/docs/aeguidelines.pdf for further clarification. *Frequency is provided based on 252 patients.* Below is the CAEPR for MLN0128 (TAK-228)(INK128).

NOTE: Report AEs on the SPEER **ONLY IF** they exceed the grade noted in parentheses next to the AE in the SPEER. If this CAEPR is part of a combination protocol using multiple investigational agents and has an AE listed on different SPEERs, use the lower of the grades to determine if expedited reporting is required.

Version 2.2, April 26, 2016

Adverse Events with Possible Relationship to MLN0128 (TAK228) (CTCAE 4.0 Term) [n= 311]			Specific Protocol Exceptions to Expedited Reporting (SPEER)
Likely (>20%)	Less Likely (<=20%)	Rare but Serious (<3%)	
BLOOD AND LYMPHATIC SYSTEM DISORDERS			
	Anemia		Anemia (Gr 2)
CARDIAC DISORDERS			
		Cardiac arrest	
		Ventricular fibrillation	
GASTROINTESTINAL DISORDERS			
	Abdominal pain		Abdominal pain (Gr 2)
	Constipation		Constipation (Gr 2)
Diarrhea			Diarrhea (Gr 2)
	Dry mouth		Dry mouth (Gr 2)
Mucositis oral			Mucositis oral (Gr 2)
Nausea			Nausea (Gr 2)
Vomiting			Vomiting (Gr 2)
GENERAL DISORDERS AND ADMINISTRATION SITE CONDITIONS			
	Edema limbs		
Fatigue			Fatigue (Gr 2)
	Fever		Fever (Gr 2)
	General disorders and administration site conditions - Other (mucosal inflammation)		General disorders and administration site conditions - Other (mucosal inflammation) (Gr 2)
INFECTIONS AND INFESTATIONS			
	Urinary tract infection		Urinary tract infection (Gr 2)
INVESTIGATIONS			
	Creatinine increased		Creatinine increased (Gr 2)

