		Electrocardiogram QT corrected interval prolonged	
	Platelet count decreased		Platelet count decreased (Gr 2)
	Weight loss		Weight loss (Gr 2)
METABOLISM AND NUTRITION DISORDERS			

Anorexia			Anorexia (Gr 2)
	Dehydration		Dehydration (Gr 2)
Hyperglycemia			Hyperglycemia (Gr 2)
	Hypokalemia		Hypokalemia (Gr 2)
	Hypomagnesemia		Hypomagnesemia (Gr 2)
	Hypophosphatemia		Hypophosphatemia (Gr 2)
MUSCULOSKELETAL AND CONNECTIVE TISSUE DISORDERS			
	Arthralgia		
	Back pain		Back pain (Gr 2)
	Pain in extremity		
NERVOUS SYSTEM DISORDERS			
	Dizziness		Dizziness (Gr 2)
	Dysgeusia		Dysgeusia (Gr 2)
	Headache		Headache (Gr 2)
PSYCHIATRIC DISORDERS			
	Insomnia		
RESPIRATORY, THORACIC AND MEDIASTINAL DISORDERS			
	Cough		Cough (Gr 2)
	Dyspnea		Dyspnea (Gr 2)
		Pneumonitis	
	Respiratory, thoracic and mediastinal disorders - Other (oropharyngeal pain)		
SKIN AND SUBCUTANEOUS TISSUE DISORDERS			
Pruritus			Pruritus (Gr 2)
Rash maculo-papular			Rash maculo-papular (Gr 2)

¹This table will be updated as the toxicity profile of the agent is revised. Updates will be distributed to all Principal Investigators at the time of revision. The current version can be obtained by contacting [contact]. Your name, the name of the investigator, the protocol and the agent should be included in the e-mail.

Adverse events reported on MLN0128 (TAK228) trials, but for which there is insufficient evidence to suggest that there was a reasonable possibility that MLN0128 (TAK228) caused the adverse event:

Cardiac disorders - Heart failure; Pericardial effusion; Sinus tachycardia

Eye disorders - Blurred vision; Eye disorders - Other (visual acuity reduced); Eye pain; Photophobia

Gastrointestinal disorders - Dyspepsia; Dysphagia; Esophagitis; Gastroesophageal reflux disease; Gastrointestinal disorders - Other (intestinal obstruction); Oral pain; Pancreatitis; Small intestinal obstruction; Small intestinal perforation; Toothache

General disorders and administration site conditions - Chills; Gait disturbance; Non-cardiac chest pain; Pain

Hepatobiliary disorders - Gallbladder obstruction

IMMUNE SYSTEM DISORDERS - Allergic reaction

Infections and infestations - Kidney infection; Lung infection; Sepsis; Skin infection; Upper respiratory infection

Injury, poisoning and procedural complications - Fall; Tracheal obstruction

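### Section 6 allows reduced-dose retreatment after Grade 4 cardiac arrest, ventricular fibrillation, QTc prolongation or pneumonitis on undefined clinical benefit, with no bar and no prior agreement

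*Combined protocol and SAP*

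**What the plan says.** Section 6 gives separate dose-modification tables for nausea, vomiting, diarrhea, hyperglycemia, and thrombocytopenia with neutropenia (the last for patients in remission only). In each, the Grade 4 instruction is "Off protocol therapy", with no exception.

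A general Non-Hematological Toxicity table follows. Its Grade 4 row makes permanent discontinuation the default, then exempts patients "unless they derive clinical benefit, in which case they may be retreated at a reduced dose level after recovery" to Grade 1 or less. The only other qualification, for isolated laboratory values of no clinical significance, relaxes the stop and does not restrict retreatment. Two footnotes apply: "Patients requiring a delay of >4 weeks if related to MLN0128 (TAK-228) should go off protocol therapy", and more than two dose reductions also end protocol therapy.

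Section 7.1.1 lists four events as rare but serious (under 3%): cardiac arrest, ventricular fibrillation, "Electrocardiogram QT corrected interval prolonged", and pneumonitis. Section 2.2.3 records the cardiac history: "A death on INK128-001 due to ventricular arrhythmia and cardiac arrest was assessed as possibly related to MLN0128 (TAK-228"). It adds that in a later dedicated QT study, treatment "was not associated with clinically meaningful effects on the overall electrocardiographic safety profile".

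**The concern.** The order of strictness looks inverted. A patient with Grade 4 vomiting must stop whatever the benefit, and so must a patient in remission with Grade 4 neutropenia. A patient who survives Grade 4 ventricular fibrillation may be re-dosed if judged to benefit. The protocol gives no reason for this ordering and does not say what counts as benefit or who decides.

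What is at stake is the safety of an individual patient: re-exposure, after recovery, to a drug that may have caused a life-threatening event whose recurrence could be fatal. The response rate, significance level, power and sample size are not involved.

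**Working it through.** The plan states no figure to reproduce. The main check is textual; the arithmetic only gives scale.

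**1. Which row governs the four events?** None has its own table in Section 6, so all four fall under the general row. By contrast, all four non-hematological toxicities that have their own table carry an unconditional Grade 4 stop.

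**2. Does anything elsewhere bar re-exposure?**

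| Provision | What it does | Bars retreatment of the patient? |
|---|---|---|
| Section 6: recovery to Grade 1 or less, reduced dose, 4-week limit, at most two reductions | Conditions on retreatment | No |
| 5.3 and 5.5 | Removal is mandatory once an event is unacceptable or the investigator judges the patient unfit to continue | Only by judgement; no event is named |
| 3.2.9 | Excludes baseline QTc above 480 ms or "history of congenital long QT syndrome or Torsades de pointes" | No; entry criterion only |
| 7.3.2 and 7.3.3 | Serious events reported to the sponsor; Grade 4 within 24 hours, with copies to the Principal Investigator | No; notification, not agreement |
| 13.5 | Counts dose-limiting toxicities for the cohort decision | No |
| 13.6.1 | Suspends accrual | No |

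**3. How much does the dose fall?** Drug per 28-day cycle, from the dose-level table: level +2, 4 × 28 = 112 mg; +1, 4 × 21 = 84 mg; 0, 3 × 21 = 63 mg; −1, 2 × 21 = 42 mg; −2, 2 × 15 = 30 mg. One-level reductions:
- 112 to 84 mg: 25%
- 84 to 63 mg: 25%
- 63 to 42 mg: 33%
- 42 to 30 mg: 29%

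A retreated patient would therefore still receive 67% to 75% of the previous cycle dose. There is no level below −2.

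**4. How many patients?** The documents give no Grade 4 rate, so both inputs are assumptions:
- *p*, the chance that a patient has any of the four events at Grade 4: 0.5% to 3%. The listing gives only under 3% per event.
- *b*, the chance of being judged to benefit: 10% to 30%, borrowing the null and target CR/CRi rates in 13.1.2.4 as a stand-in.

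Per-patient chance *q* = *p* × *b*: 0.005 × 0.10 = 0.0005 to 0.03 × 0.30 = 0.009.

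| | n = 26 | n = 35 (maximum accrual) |
|---|---|---|
| Expected number, n × *q* | 0.013 to 0.234 | 0.0175 to 0.315 |
| At least one, 1 − (1 − *q*)^n | 1.3% to 20.9% | 1.7% to 27.1% |

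Given *p* and *b*, these are upper bounds, because *q* leaves out survival, recovery to Grade 1 or less within 4 weeks for a related event, and having a dose reduction left. If 20% to 50% of such patients met those conditions (a further assumption), *q* would run from 0.0005 × 0.2 = 0.0001 to 0.009 × 0.5 = 0.0045. The chance of at least one in 26 would then be 1 − 0.9999^26 = 0.3% to 1 − 0.9955^26 = 11%.

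**The case against.** The strongest reply is that stopping is already the default and retreatment is optional and hedged. The patient must be benefiting, must have recovered, must go to a lower dose, and must not exceed the delay or reduction limits. The investigator can stop treatment at any time under 5.3. None of the four events has an exemption from expedited reporting in 7.1.1, so the sponsor would normally know before re-dosing. Section 2.2.3 also provides for ECGs during treatment when clinically appropriate. With a cited median survival of 3 months in relapsed ALL (Section 2.1), leaving rechallenge of a responder to judgement is defensible. All of this stands as mitigation. None of it bars re-exposure after the four events or requires anyone outside the site to agree first.

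Three stronger readings are tempting, and the documents do not support them.
- *Section 6 contradicts itself, so two sites could treat the same Grade 4 vomiting differently.* If the general table also covered toxicities that have their own table, lower grades would clash too: Grade 2 hyperglycemia needs no change in its own table but a hold in the general one. Only a residual reading works. The heading could say so, but that is a clarification.
- *The drug has a general QT problem that the plan ignores.* The dedicated study found no clinically meaningful ECG effect. The concern is confined to re-exposing a patient who has already had the event.
- *The entry bar on Torsades de pointes shows that retreatment is inconsistent with the plan.* That criterion concerns entry and a different event; it does not address continuing a patient already on treatment.

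**Conclusion.** The point holds as a gap in individual patient safety. Read as the residual table, the general Grade 4 row permits, without requiring, reduced-dose retreatment after any of the four rare-but-serious events, while four other non-hematological toxicities are absolute stops at Grade 4. The existing limits reduce the risk but do not close the gap.

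It is small in frequency and serious in consequence. The expected number of affected patients is well below one. A reader might take 20.9% as the likely chance of a retreatment in 26 patients. It is the top of a range built on assumed event and benefit rates, with three of the protocol's own conditions left out. Because benefit is undefined, the stand-in for it is also uncertain. The case for acting rests on the severity of a recurrence and the low cost of the change. Nothing in the primary analysis is affected.

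**What to change.** 1. Add to the Grade 4 row: *Permanently discontinue, without exception, after Grade 4 cardiac arrest, ventricular fibrillation, QTc prolongation or pneumonitis at least possibly related to study drug.*
2. For any other Grade 4 event in this table, keep the clinical-benefit exception but allow retreatment only after discussion with the study PI and CTEP monitor. Section 5 already uses that mechanism for patients in PR after two cycles. A documented CR, CRi, PR or MLFS should not be required, since that would shut out patients whose event comes before their first response assessment.
3. As a clarification, head the table *Non-hematological toxicities without their own table above*. This wording keeps fatigue, electrolyte, liver-test and infectious toxicities in the table; they are named in the paragraph before it but have no table of their own.

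The cost is one table row and one heading. Sample size, primary analysis and the 13.6.1 stopping rule stay as they are. The downside is that a rare responder with one of the four events loses the option of retreatment (at most 0.01 to 0.23 expected of 26, on the assumptions above), which matters to that patient given the prognosis.
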